7.8.5 Prior and Concomitant Medications

Prior medications are defined as medications that stop prior to the first dose of study drug. Concomitant medications are defined as medications that (1) start before the first dose of study drug and are continuing at the time of the first dose of study drug, or (2) start on or after the date of the first dose of study drug.

Prior and concomitant medications will be coded using the World Health Organization (WHO) Drug Enhanced Dictionary (March 2018 Version) and listed by reported term and Anatomical Therapeutic Class (ATC) classification. Medications will be listed by subject including the start and end dates, or whether it is ongoing, dose, unit, and indication.

7.8.6 Vital Sign Measurements

Vital sign measurements will be summarized at baseline and at each time point. For each summary the number, mean, median, standard deviation, minimum, and maximum values will be presented by treatment and study phase.

7.8.7 Physical Exam

Physical examination data will be listed.

7.8.8 Electrocardiogram (ECG)

ECG parameters will be summarized by treatment group using descriptive statistics. In order to assess the QT interval data, corrected QT (QTc) values will be calculated based on the following methods.

- 1) Fridericia's correction: $QTc = QT/RR^{0.33}$,
- 2) Bazett's Correction: $QTc = QT/RR^{0.5}$,

QTc interval data at post-baseline visits will then be summarized descriptively by central tendency techniques. In addition, the frequency counts and percentages by treatment group for the following categories will be provided:

- >450 with Baseline <=450,
- >480 with Baseline <=480,
- >500 with Baseline <=500,

Increases from baseline > 30 and

Increases from baseline > 60.

7.9 Clinical biology

Only a portion of clinical biology data will be available at the time of database lock. Final clinical biology analysis/summary outputs will be generated when all clinical biology data are available.

7.10 Statistical and analytical issues

7.10.1 Handling of Dropouts or Missing Data

Missing data will be handled using the Worst-Case analysis method for the primary and key secondary endpoints. In the Worst-Case analysis, subjects with fewer than 4 days of diary data in a given week will be considered non-responders for that week. Additionally, subjects with missing SES-CD data will be classified non-responder for that measure in that week.

The following three sensitivity analyses will be conducted to address the impact of missing data on the primary and key secondary endpoints:

7.10.2 Last Observation Carried Forward (LOCF) Analysis

In the first analysis, missing values will be replaced with the last previous non-missing value. The baseline values will not be carried forward.

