#### **4.5 Premature Subject Discontinuation**

Subjects will be encouraged to complete the study; however, they may voluntarily withdraw at any time. Subjects withdrawn from the study will not be replaced.

A subject may be discontinued from study drug treatment and/or the study for the following reasons:

- Occurrence of an AE and/or SAE, which suggests an unacceptable risk to the subject, in the judgment of the investigator, including worsening of the disease under study.
- Pregnancy (see Section 7.7 for further details).
- Subject request to withdraw.
- Sponsor decision to terminate the study.

For all cases of premature withdrawal from the study listed above or any other, the investigator must provide the reason for discontinuation on the appropriate CRF page. *The investigator should make every attempt to obtain End of Treatment and End of Study assessments, including ileocolonoscopy.*

If treatment with investigational study drug has been prematurely discontinued, the End of Treatment assessments will be completed, and an attempt should be made to have the subject followed for 14 days after last administration of study drug to perform the End of Study assessments.

If a subject prematurely discontinues treatment with investigational drug at any time due to an AE or SAE, the End of Treatment assessments will be completed, and an attempt should be made to have the subject followed at least 14 days to perform the End of Study assessments, or until resolution or stabilization of the condition resulting in withdrawal has been confirmed.

The Investigator may discontinue individual subjects from the study at any time during the study. The investigator must provide the reason for discontinuation on the appropriate CRF page.

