### 8.7.2 Handling of Dropouts or Missing Data

Missing data will be handled using the Worst Case analysis method for the primary and key secondary endpoints. In the Worst Case analysis, subjects with fewer than 4 days of diary data in a given week will be considered non-responders for that week. Additionally, subjects with missing SES-CD data will be classified non-responder for that measure in that week.

The following three sensitivity analyses will be conducted to address the impact of missing data on the primary and key secondary endpoints:

**Last Observation Carried Forward (LOCF) Analysis:** In the first analysis, missing values will be replaced with the last previous non-missing value. The baseline values will not be carried forward.

**Multiple Imputation Analysis:** In the second analysis, missing values will be filled in by the multiple imputation method which involves the following distinct phases:

- The missing data will be filled in to generate complete data sets using SAS/STAT procedure PROC MI;
- The complete data sets will be analyzed using PROC LOGISTIC in SAS/STAT;
- The above two steps will be repeated 5 times;
- The results from the complete data sets will be combined for statistical inference using SAS/STAT procedure PROC MIANALYZE.

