| CDAI assessment calculated by EDC                          | X                              |                                   | X                       | X                    | X   |                      | X              |  |                   |
| Ileocolonoscopy (SES-CD) c                      | X                              |                                   |                         | X                    |   |                      | X              |  |                   |
| IBDQ and WPAI-CD   |                                | X                                 |                         | X                    | X (V10 and V13 only)                            |                      | X              |  |                   |
| Electronic Daily Diary Instructions/Completion             | X                              | X                                 | X                       | X                    | X   |                      | X              |  |                   |
| Randomization  |                                | X                                 |                         |                      |   |                      |                |  |                   |
| Dispense Study Drug  |                                | X (1st dose at clinic) | X (except V3)           | X                    | X   |                      |                |  |                   |
| Study Drug Collection/Compliance                           |                                |                                   | X                       | X                    | X   | X                    |                |  |                   |

- a. Perform a full physical examination at Screening (Visit 1), prior to the Long Term Treatment Phase (Visit 7), and at End of Treatment (Visit 16); perform disease and symptom driven physical examination (including assessments for abdominal mass and extraintestinal manifestations of Crohn's disease based on CDAI – see Appendix 2) at other visits.
- b. Including *C. difficile* safety testing as described in Section 6.3.5
- c. The baseline ileocolonoscopy will be performed between Day -12 and Day -5; it will provide the baseline SES-CD, and will be used to assess Inclusion Criterion #3. Bowel prep will be dispensed at Visit 1. Ileocolonoscopy to be completed within 7 days after Visit 7 and Visit 16. Bowel prep will be dispensed at Visit 7 and Visit 16, cleansing regimen to begin after Visit 7 and Visit 16 assessments.

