5 STUDY OVERVIEW

5.1 Study Design

RECD3125 and RECD3126 are double-blind, placebo-controlled, parallel-group, multicenter, multiregional, 52-week studies to assess the efficacy and safety of Rifaximin DR tablets for the induction of clinical remission and endoscopic response at 16 weeks followed by clinical and endoscopic remission after 52 weeks of continuous therapy in subjects with active moderate Crohn's disease. Subjects with active, moderate disease defined by a CDAI score of ≥ 220 and ≤ 450 points at screening, and evidence of active ileocolonic Crohn's disease defined by a minimum SES-CD of 7 determined during baseline ileocolonoscopy will be eligible for the study. Eligible subjects will complete a 2- to 3-week Screening Period, a 52-week Treatment Period consisting of a 16-week Induction Phase and 36-Week Long Term Treatment Phase, and a 2-week Follow-up Period. Subjects who successfully complete the 2- to 3-week Screening Period and qualify based on CDAI and SES-CD scores will enter the 52-week Treatment Period of the trial and will be randomized in a 1:1 allocation to Rifaximin DR 800 mg BID or placebo. Randomized subjects will have subsequent ileocolonoscopies conducted at the end of the Induction Phase (between Weeks 16 and 17), and following completion of the 36-week Long Term Treatment Phase (Week 52) to assess the effects of treatment on the degree of mucosal healing. Assessments of efficacy and safety will be performed during clinic visits at Weeks 0

(baseline), 2, 4, 8, 12, and 16; then every four weeks through Week 52. All subjects will complete a 2-week (study drug free) Follow-up Period following completion of the 52-week Treatment Period and will return to the clinic for final assessments (End-of-Study [EOS] visit; Week 54). See Figure 1.

Figure 1 Design Schematic

*Baseline ileocolonoscopy can be scheduled at screening visit, or while collecting CDAI data. Performed only after CDAI eligibility confirmed; SES-CD score determined by central endoscopy laboratory

**Ileocolonoscopy performed; SES-CD score determined by central endoscopy laboratory.

***CDAI eligibility based on results of diary data. Hematocrit value, extraintestinal complications, body weight, and abdominal mass are assessed at Visit 1.

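### LOCF adds almost nothing for a missing Week 16 SES-CD, and it is the only one of the three promised sensitivity analyses that the SAP describes

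*SAP*

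**What the plan says.** The main rule for the primary and key secondary endpoints is in SAP 7.10.1: "subjects with missing SES-CD data will be classified non-responder for that measure in that week". The same section then states: "The following three sensitivity analyses will be conducted to address the impact of missing data on the primary and key secondary endpoints".

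SAP 7.10.2 gives the first of the three: "In the first analysis, missing values will be replaced with the last previous non-missing value". It adds: "The baseline values will not be carried forward". The next section, 7.10.3, deals with partial dates, so the SAP never sets out a second or third analysis.

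Protocol 8.7.2 does. After LOCF it continues: "In the second analysis, missing values will be filled in by the multiple imputation method which involves the following distinct phases". Its third is an observed-case analysis, worded around a 4-week assessment period. SAP section 8, which lists planned evaluations that will not be performed, names neither.

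On timing, protocol Appendix 1 says: "The baseline ileocolonoscopy will be performed between Day -12 and Day -5". SAP 5.1 says: "Randomized subjects will have subsequent ileocolonoscopies conducted at the end of the Induction Phase (between Weeks 16 and 17", and places the last one at Week 52. Outside that schedule, protocol 4.5 says of premature withdrawal: "The investigator should make every attempt to obtain End of Treatment and End of Study assessments, including ileocolonoscopy".

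**The concern.** A sensitivity analysis for missing data is useful if it rests on a different assumption from the main analysis. For the diary endpoints LOCF does that, because earlier weeks exist. For Week 16 SES-CD the only earlier scheduled score is the one the rule excludes, so a subject who misses the scope, or withdraws without one, has nothing to carry forward.

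At Week 52 the difficulty is the reverse. A value may exist, but it can be 36 weeks old. A subject who drops out without rescue, surgery or a withdrawal scope, and whose Week 16 SES-CD was 2 or less, counts as a Week 52 endoscopic remitter.

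This matters because the main rule is called Worst-Case yet treats both arms alike. If placebo loses more subjects for reasons unrelated to the mucosa, scoring missing as failure lowers the placebo rate more and can create an apparent effect. LOCF as specified would seldom reveal that.

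**Working it through.** **1. What LOCF can fill**

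| Missing score | Last earlier scheduled score | May it be carried? | Other source |
|---|---|---|---|
| Week 16 SES-CD | Baseline (Day -12 to Day -5) | No | Withdrawal scope, if obtained |
| Week 52 SES-CD | Weeks 16–17 | Yes, over 52 − 16 = 36 weeks | Withdrawal scope, if obtained |

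Neither document says whether, or in what time window, a withdrawal scope counts for Week 16. Neither says whether a subject whom LOCF leaves unfilled is a non-responder or is excluded.

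**2. The plan's own figure.** Protocol 8.2 assumes 40% against 55%, two-sided alpha 0.05 and about 240 per arm. With d the difference in rates, s0 the pooled and s1 the unpooled standard error, power = Φ((d − 1.96·s0)/s1) + Φ((−d − 1.96·s0)/s1). Here s0 = 0.0456, s1 = 0.0451, and power = Φ((0.150 − 0.0894)/0.0451) = 0.911; the second term is negligible. The stated 90% or more is reproduced.

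**3. How far LOCF moves the estimate.** Take the planning rates, 330 per arm and an assumed 20% missing (0.20 × 330 = 66 per arm).

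- Main rule: 0.40 × 0.80 = 32.0% against 0.55 × 0.80 = 44.0%, a difference of 12.0 points.
- LOCF, no withdrawal scopes, unfilled subjects counted as failures: identical, 12.0 points.
- LOCF, half of the missing scoped, responding at half the completers' rate: 0.320 + 0.40 × 0.5 × 0.10 = 34.0% against 0.440 + 0.55 × 0.5 × 0.10 = 46.75%, a difference of 12.75 points.
- LOCF, half scoped, responding at the completers' rate: 36.0% against 49.5%, a difference of 13.5 points.
- Observed case: 40% against 55%, a difference of 15.0 points.

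The documents do not give the share of withdrawals that would be scoped; one half is an assumption.

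**4. What unequal loss does under the main rule.** Assume true response of 45% in both arms, missingness unrelated to outcome, and 330 per arm. An unstratified two-proportion test stands in for the CMH test.

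- Missing 25% (placebo) and 15% (drug): 0.45 × 0.75 = 33.75% against 0.45 × 0.85 = 38.25%, so d = 0.045. With s0 = 0.0374 and s1 = 0.0373, rejection = Φ(−0.757) + Φ(−3.17) = 0.225.
- Missing 22% and 18%: 35.1% against 36.9%, d = 0.018. Rejection = Φ(−1.48) + Φ(−2.44) = 0.077.

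SAP 7.3 says that both studies will be terminated early, so the same 25%/15% case at smaller illustrative sizes is:

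| Per arm | Rejection |
|---|---|
| 330 | 22.5% |
| 165 | 13.6% |
| 150 | 12.8% |
| 100 | 10.1% |
| 50 | 7.5% |

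If LOCF could use withdrawal scopes for a quarter or half of the missing subjects at 330 per arm, with the same 45% response and the rest failures, it would reject 14.5% or 9.0% of the time.

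**The case against.** A reader might infer that the endoscopic co-primary has no working missing-data check at all. The documents do not support that. Protocol 8.7.2 plans multiple imputation and observed case, the SAP still promises three sensitivity analyses, and section 8 drops neither of the missing two. In the example in step 4, missingness is unrelated to outcome. Observed case would then compare 45% with 45% and reject near 5%, which would expose the artefact. The gap is that the SAP does not carry these analyses over. As the protocol words them, they also need work before they can be run: no imputation model is given, and a 4-week assessment period does not fit a single endoscopy.

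It is also too strong to say that LOCF can never fill a Week 16 score. Protocol 4.5 asks sites to attempt an ileocolonoscopy at withdrawal, and where one exists LOCF has a value to carry. That part of the objection stands, although the scope is only an attempt and no rule links its score to Week 16.

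Nor is 22% the false-positive rate of the trial. The 45% response rate and the missing rates are assumptions, 330 per arm will probably not be reached, and SAP 7.7.1.1 requires both co-primaries to be significant. Reading the protocol's 20% drop-out factor as an induction-phase rate is likewise an inference. It is consistent with 210/(0.8 × 0.8) = 328, close to 330, but protocol 8.2 gives one figure for both phases.

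Finally, carrying Week 16 to Week 52 is what LOCF ordinarily does, and rescued or operated subjects stay failures. Both are true, but 36 weeks is a long gap for remission in a relapsing disease.

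**Conclusion.** The point holds in limited form. For Week 16 SES-CD, LOCF differs from the main analysis only through withdrawal scopes, or through an unstated decision to exclude unfilled subjects. It is also the only missing-data sensitivity analysis that the SAP specifies. At Week 52 it can turn an old Week 16 score into a current remission.

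With 20% missing, LOCF shifts the estimated difference by 0 to 1.5 points when none to half of the missing are scoped and the unfilled count as failures. Observed case shifts it by 3.0 points. The main rule is not conservative when placebo loses more. At 330 per arm, the assumed 10-point imbalance in missingness raises rejection on this one endpoint from 5% to about 22%, and a 4-point imbalance to about 8%. Both figures fall with smaller samples, and neither is an error rate for the induction claim.

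**What to change.** For the SES-CD endpoints, replace LOCF in SAP 7.10.2 by a two-way tipping-point analysis:

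- keep rescued or operated subjects as failures, as already planned;
- use withdrawal scores under a stated rule, including the time window in which they count;
- vary the response rate of the remaining missing subjects separately by arm, including the corner where missing drug subjects fail and missing placebo subjects respond;
- report where the CMH p-value crosses 0.05.

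That corner is a bound, not a test to be passed. With the planning rates, 20% missing and no withdrawal scores or rescues, it gives 44% on drug against 32% + 20% = 52% on placebo. What informs the reader is where the crossing lies and whether rates there are plausible.

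Also restore the protocol's observed-case and multiple-imputation analyses in the SAP, with an imputation model and with observed case worded for a single endoscopy, or list them as dropped in section 8. LOCF may stay for the diary endpoints.

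The cost is a few lines of SAP text and a little more programming, chiefly one grid. No new data are needed.

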7.10.3 Imputation Rules for Partial or Missing Dates

Imputation of partial dates will be made for AE onset and stop dates, start and end dates of concomitant medication, start date of subsequent anticancer therapy, date of initial diagnosis and death date. If dates are completely missing, no imputation will be made. For any partial date with missing year, no imputation will be made.

The general rule for imputation is:

- If only day is missing, then the 15th of the month will be used.
- If only year is present, then June 30th will be used.

If such imputation date for initial diagnosis is on or after date of first dose, then date of first dose – 1 will be used. If such imputed date for subsequent anticancer therapies is before date of last dose, then date of last dose + 1 will be used. If the imputed date is for an AE start date and is in the same year and month as but before the first dose date, then the first dose date will be used, or if the imputed AE start date is after the AE end date, then the AE end date will be used. If the imputed date is for an AE start date and is in the same year and month as but after the last dose date + 30 days, then the last dose date + 30 days will be used.

If the imputed date is for an AE end date and is after the death date, then the death date will be used, or if the imputed AE end date is before the AE start date, then the AE start date will be used.

Every effort will be made to obtain complete dates for deaths. If both month and day are missing for death date or a death date is totally missing, do not impute and censor the subject survival time. If death year and month are available but day is missing, the following algorithm will be used:

- If mmYYYY for last contact date = mmYYYY for death date, set death date to the day after the last contact date.
- If mmYYYY for last contact date < mmYYYY for death date, set death date to the first day of the death month.
- If mmYYYY for last contact date > mmYYYY for death date, data error and do not impute.

7.11 Multiplicity

The study has a single primary endpoint as the primary hypothesis, therefore no multiplicity adjustment is needed to the overall significance level of 0.05. Additionally, the clinical trial will be providing data for two separate indications (induction and long term treatment) with each indication having its own separate endpoint. On that basis, no multiplicity adjustment is needed to the overall significance level of 0.05 per indication because conclusions will be reached independently for induction and separately for long term treatment.

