### 2.2.2 Key Secondary Endpoints

The key secondary endpoint is clinical and endoscopic remission. Two key co-secondary endpoints of efficacy will assess this endpoint during the Long Term Treatment Phase. The first is:

- Clinical symptom remission defined by (1) the total number of liquid/very soft stools for the 7 days prior to the Week 52 visit being  $\leq 10$  (from CDAI Item 1); AND (2) an abdominal pain rating of  $\leq 1$  (from CDAI Item 2) on each day for the 7 days prior to the Week 52 visit.

The second is:

- Endoscopic remission defined as a SES-CD score of  $\leq 2$  at Week 52. SES-CD scores will be calculated from centrally-read digital video of ileocolonoscopies performed at Week 52.

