#### **8.7.5      Multiple Comparisons/Multiplicity**

The study has a single primary endpoint as the primary hypothesis, therefore no multiplicity adjustment is needed to the overall significance level of 0.05. Additionally, the clinical trial will be providing data for two separate indications (induction and long term treatment) with each indication having its own separate endpoint. On that basis, no multiplicity adjustment is needed to the overall significance level of 0.05 per indication because conclusions will be reached independently for induction and separately for long term treatment.

The complete evaluation of clinical efficacy in this study requires the study of multiple key secondary efficacy variables collected at numerous time points. It is therefore necessary to properly and sensitively control the probability of making erroneous conclusions based solely upon compounding the likelihood of a type I error. The issue of multiplicity of secondary measurements will be handled by statistical testing of these outcomes in a hierarchical fashion. The order of secondary endpoints for the Induction and Long Term Treatment Phases are described in Sections 2.2.2 and 2.2.3. Significance tests will be conducted until a non-significant p-value is found ( $p > 0.05$ ). Once a non-significant p-value occurred, all subsequent significance tests will be considered exploratory in nature.

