2 INTRODUCTION

The purpose of this statistical analysis plan (SAP) is to provide details of the statistical analyses that have been outlined within the protocols of Rifaximin delayed release studies including *RECD3125* and *RECD3126*. The scope of this plan includes the final analysis. Any changes to the methods described in this SAP will be documented in each clinical study report (CSR).

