7.3 Sample Size

For sample size justification, reference corresponding study protocols.

Originally planned sample sizes per arm for each of the studies are listed below:

Study	Treatment A: Rifaximin DR Tablets 800 mg BID	Treatment B: Placebo BID
RECD3125	330	330
RECD3126	330	330

Both studies will be terminated early therefore the actual sample size may vary.

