7.7.1 Primary Efficacy Analysis

7.7.1.1 Induction Phase

There will be two co-primary measures of efficacy assessed during the Induction Phase. The first co-primary endpoint is:

- Clinical symptom remission defined by (1) the total number of liquid/very soft stools for the 7 days prior to the Week 16 visit being ≤ 10 (from CDAI Item 1); AND (2) an

abdominal pain rating of ≤ 1 (from CDAI Item 2) on each day for the 7 days prior to the Week 16 visit.

The second co-primary endpoint is:

- Endoscopic response defined as a ≥ 3 -point decrease in the SES-CD from baseline to the SES-CD score obtained between Week 16 and Week 17. SES-CD scores will be calculated from centrally-read digital video of ileocolonoscopies performed at baseline and between Week 16 and Week 17.

For each endpoint, the null hypothesis $H_0: \pi_R - \pi_P = 0$ versus the alternative $H_A: \pi_R - \pi_P \neq 0$ is of interest, where π_R is the binomial parameter for induction of remission/response for the Rifaximin DR group, and π_P is the binomial parameter for induction of remission/response for the placebo group. Subjects who require the initiation of rescue medication and/or surgery for CD will be considered treatment failures from the date of the introduction of the rescue medication and/or surgery, regardless of their actual response data. The Cochran-Mantel-Haenszel (CMH) test, stratified by country, will be used to test the hypothesis. Each null hypothesis of no difference will be rejected if the resulting p-value for the respective statistical test is less than 0.05. Significance for the induction claim will only be declared if both null hypotheses are rejected. As such, the overall Type I error rate will be maintained at the 5% level without adjustment for multiple comparisons.

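### SAP 7.11 leaves out the protocol's stop-at-first-failure order for the secondary endpoints, and Section 8 does not declare the change

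*SAP*

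**What the plan says.** Protocol 8.7.5 has two paragraphs. The first argues that the primary hypothesis needs no adjustment and that induction and long-term treatment are separate indications, each at 0.05. The second says error control across the secondary variables is necessary: "The issue of multiplicity of secondary measurements will be handled by statistical testing of these outcomes in a hierarchical fashion". It takes the order from the endpoint lists: "The order of secondary endpoints for the Induction and Long Term Treatment Phases are described in Sections 2.2.2 and 2.2.3". Testing stops at the first p above 0.05: "Once a non-significant p-value occurred, all subsequent significance tests will be considered exploratory in nature". Section 2.2.2 holds the Week 52 pair ("Two key co-secondary endpoints of efficacy will assess this endpoint during the Long Term Treatment Phase"), so read literally that pair comes first and the 2.2.3 list follows.

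SAP 7.11 reproduces the first paragraph, including "On that basis, no multiplicity adjustment is needed to the overall significance level of 0.05 per indication", and stops there. SAP 4.3 keeps the protocol's list sequence but does not call it a test order. SAP 7.7.2.1 analyses the binary secondaries by the primary method, for which 7.7.1.1 says: "Each null hypothesis of no difference will be rejected if the resulting p-value for the respective statistical test is less than 0.05". The one gate, at the end of 7.7.2.4, makes all secondaries descriptive if the primaries are not significant. Section 8 lists the planned evaluations that are dropped, down to a single QT correction, and does not mention the hierarchy.

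**The concern.** The quoted sentence in 7.11 is not itself the fault. It is protocol text about the two indications. The fault is the missing paragraph after it. If both co-primaries are significant, the SAP gate is open and no SAP text orders or limits the secondary tests. An endpoint low in the list could then be reported as significant although one above it failed. The protocol would call that result exploratory. Two people working from the two documents could disagree on which secondary p-values support a claim, and the disagreement would surface after the results are known.

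**Working it through.** **1. The SAP's own figure.** Each co-primary is tested two-sided at 0.05 and both must be rejected (7.7.1.1). The maximum type I error of such a pair is 0.05. The same holds for the Week 52 pair (7.7.1.2). The 0.05 per indication therefore reproduces, and the omission does not touch it.

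**2. What each document provides for the secondaries.**

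| Element | Protocol 8.7.5 | SAP |
|---|---|---|
| Order of testing | 2.2.2, then 2.2.3 | none stated |
| Stopping rule | first p > 0.05 | none stated |
| Status of later tests | exploratory | not addressed |
| Gate on the primaries | not stated in this section | 7.7.2.4 |
| Change declared | n/a | not in Section 8 |

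**3. How many tests the gap covers.** SAP 7.7.2.1 has seven bullets: CDAI below 150 at Week 16; symptom remission at 80% or more of visits; the pain component; the stool component; SES-CD of 0 at Week 52; CDAI remission by visit; and the 100-point CDAI response by visit. Four of them (pain, stool, CDAI remission, CDAI response) refer to post-baseline time points without naming one. The Week 16 CDAI bullet is one time point of the later CDAI-remission bullet. With one test per bullet and a different visit for that later bullet, the ceiling is seven. Sections 7.7.2.2 to 7.7.2.4 state no significance level for their treatment comparisons, so they are not counted.

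**4. Illustration.** Suppose the gate is open and m of these endpoints are truly null, with one test each at two-sided 0.05. If independent, P(at least one false positive) = 1 − 0.95^m:

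- m = 3: 1 − 0.8574 = 14.3%
- m = 7: 1 − 0.6983 = 30.2%

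For equally correlated normal test statistics (numerical integration):

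| m | correlation 0 | 0.5 | 0.8 |
|---|---|---|---|
| 3 | 14.3% | 12.5% | 9.8% |
| 7 | 30.2% | 23.0% | 14.9% |

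The values of m and the correlations are assumptions; the documents give neither. The null secondaries are treated as independent of the co-primary tests. A fixed sequence with one test per step holds every cell to at most 5%, because under the complete null a false positive requires the first step to be rejected.

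**5. Whether the protocol paragraph can simply be pasted back.** It cannot, for three reasons.

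- It places the Week 52 pair at the head of one order, while 7.11 has the two indications concluded independently and 7.7.1.2 tests the pair with no gate.
- It orders endpoints but names no visits.
- The third and fourth endpoints in SAP 4.3 use the durable-response definition of 7.7.2.2, which contradicts itself. Durability means response lasting through Week 52, yet the worked example says a responder at Week 52 did not achieve it.

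**The case against.** The strongest reply is that the protocol rule still governs. SAP Section 2 says its purpose is "to provide details of the statistical analyses that have been outlined within the protocols", SAP 4.3 keeps the protocol's sequence, and the Section 8 list is introduced by a word that need not mean it is complete. This stands in part. A reader might infer that the SAP abolishes the hierarchy, and the documents do not show that. They show silence. But the reply needs the reader to supply a rule that the SAP's own multiplicity section leaves out, while its changes section is otherwise detailed. A testing rule should not rest on that.

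A second reply is that several true nulls are unlikely once both co-primaries have succeeded. Pain and stool are components of the first co-primary, symptom remission over time is the same composite, the CDAI measures contain both items, and SES-CD of 0 uses the second co-primary's scale. This also stands. It is why small m is more plausible and seven is only a ceiling. A reader might take 30% as the trial's expected false-positive rate; the documents do not support that.

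A third is that the trial is ending early ("Both studies will be terminated early therefore the actual sample size may vary"), so the gate may well not open. That lowers the practical weight. It does not remove the gap, since the SAP still plans inferential tests if the gate opens.

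**Conclusion.** The omission and its non-declaration are established by the text. The consequence is conditional: only if both co-primaries are significant are the seven binary secondaries each judged at 0.05 with no order. Under the stated assumptions the chance of at least one false positive runs from about 10% to 14% for three true nulls, and from about 15% to 30% at the ceiling of seven, against at most 5% under a workable fixed sequence. A reader might infer that the induction claim or the Week 52 pair loses error control. Neither does, since each keeps its both-must-be-significant rule. Freedom to choose among visits is a separate weakness inherited from the protocol. The change should be made, but it is a clarification of which secondary results can be claimed and not a threat to the primary conclusion.

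**What to change.** Make one of two changes before unblinding.

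**Declare the removal.** This is the simpler choice given early termination. Add to Section 8: *Protocol 8.7.5's hierarchical testing is not applied; every p-value for a Section 4.3 endpoint is nominal and descriptive.* State there that the Section 4.2 Week 52 pair stays at 0.05, both required, under 7.7.1.2.

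**Or write a sequence that can be run.** Add to 7.11: *If both co-primary hypotheses are rejected, the Section 4.3 endpoints are tested at two-sided 0.05 in listed order, each at one named time point with one named test. Testing stops at the first p > 0.05. Later results and unnamed visits are descriptive.* The choice of time points is the sponsor's. Make the two durable-response steps descriptive unless 7.7.2.2 is reconciled, and the three time-to-event steps descriptive unless a between-arm test is named. If all five become descriptive, 15 − 5 = 10 listed endpoints remain. Then state where the Week 52 pair sits:

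- At the head of the sequence, as protocol 8.7.5 orders it. In that case amend the sentence in 7.11 on independent conclusions and add the gate to 7.7.1.2.
- Separate at 0.05 per indication. The 5% limit then covers the 4.3 sequence only; pair plus sequence can reach 1 − 0.95² = 9.75% if independent.

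In either case, replace the reference in 7.11 to a single primary endpoint with the both-must-be-significant rule of 7.7.1.1.

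The cost is SAP wording and lost claims. Under the sequence, lower-ranked endpoints and unnamed visits lose stand-alone significance. Steps needing Week 52 data come early, so sparse late data could end testing before the pain and stool steps. Under the declaration, no Section 4.3 endpoint can be claimed as significant.
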